10.1 Definitions and Derived Variables

10.1.1 Age

Age (years) will be calculated as the number of years between date of birth and date of informed consent, expressed as an integer.

10.1.2 Study Day

Study Day, which follows the CDISC SDTM standard, is defined as (Assessment date – date of first study drug dosing) + 1, where the assessment date is on or after the date of first study drug dosing; (Assessment date – date of first study drug dosing), where the assessment date is before the date of first study drug dosing.

10.1.3 Estimated Glomerular Filtration Rate

eGFR data will be used in data analysis. The eGFR value will be calculated using the Chronic Kidney Disease Epidemiology Collaboration (CKD-EPI) formula from both serum creatinine and serum cystatin C that will be reported from the central laboratory. The primary analysis for change in eGFR will be based on serum creatinine. Because of the potential for changes in muscle mass related to bicarbonate correction, eGFR calculated from serum cystatin C levels will be evaluated at baseline and Week 12.

The CKD-EPI formula can be expressed as a single formula using serum creatinine (mg/dL):

$$\text{eGFR} = 141 \times \min(\text{Serum Creatinine}/\kappa, 1)^\alpha \times \max(\text{Serum Creatinine}/\kappa, 1)^{-1.209} \times 0.993^{\text{Age}} \times 1.018 \text{ [if female]} \times 1.159 \text{ [if black]}$$

Where κ is 0.7 for females and 0.9 for males, α is -0.329 for females and -0.411 for males, min indicates the minimum of S_{Cr}/κ or 1 and max indicates the maximum of S_{Cr}/κ or 1

The CKD-EPI formula can be expressed as a single formula using serum cystatin C (mg/L):

$$\text{eGFR} = 133 \times \min(\text{Serum cystatin C}/0.8, 1)^{-0.499} \times \max(\text{Serum cystatin C}/0.8, 1)^{-1.328} \times 0.996^{\text{Age}} \times 0.932 \text{ [if female]}$$

10.1.4 Anion Gap

Serum anion gap will be derived as [serum sodium (mEq/L) + serum potassium (mEq/L)] – [serum chloride (mEq/L) + serum bicarbonate (mEq/L)]. Urine anion gap will be derived as urine sodium (mEq/L) + urine potassium (mEq/L) – urine chloride (mEq/L).

10.1.5 Multiple Records at a Time Point

For analysis purposes, the mean value of multiple measurements collected at the same position (i.e., supine, standing, etc.) on the same visit day will be summarized for the corresponding protocol defined time point. All collected measurements and the mean values will be listed.

10.1.6 Baseline Values

Baseline values for all efficacy and safety variables are defined as the last non-missing assessment prior to the first dose of study drug, unless otherwise specified.

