- ^b Screening 1 Visit must occur within 2 weeks of Baseline Visit.
- ^c Screening 1 and Screening 2 Visits must occur at least 5 days apart.
- ^d At Screening 1 Visit, record all prescription and non-prescription medications and nutritional supplements taken within 28 days.
- ^e Vital signs include: blood pressure and respiratory rate (both in triplicate, measurements taken approximately 2 minutes apart at Screening 1, Screening 2, and Week 12 Visits; once at all other time points), heart rate, and temperature.
- ^f Height will only be collected at the Screening 1 Visit.
- ^g Complete physical examination will include an examination of cardiovascular, lungs and chest, head and neck, abdomen, musculoskeletal, skin and neurological systems (genitourinary examination not required).
- ^h ECG will be collected in triplicate, 30 seconds apart. The subject must be in a supine position, or in the most recumbent position possible, in a rested and calm state for at least 5 minutes before the ECG assessment is conducted. All ECGs should be performed prior to blood draws whenever possible.
- ⁱ The i-STAT G3+ cartridge must be used and measurement taken from a whole blood sample within 10 min of the blood draw.
- ^j Either enzymatic or venous blood gas assay but consistent for each subject as soon as possible in accordance with local laboratory requirements.
- ^k For subjects receiving vitamin K antagonists or factor Xa inhibitors only. Vitamin K antagonists include warfarin and acenocoumaral. Factor Xa inhibitors include apixaban, rivaroxaban, betrixaban, edoxaban and enoxaparin.
- ^l If necessary, at the Screening 2 Visit, eGFR may be assessed based on local serum creatinine measurement to confirm eligibility.
- ^m For women of childbearing potential, blood samples will be collected for serum pregnancy tests at the Screening 1, Week 6, and Week 12 Visits, and a urine sample will be collected for a urine dipstick pregnancy test at the Baseline Visit.
- ⁿ Blood and urine samples will be collected and stored under frozen conditions as specified in the laboratory manual.
- ^o Instruct subjects on collecting 24-hour urine samples prior to Baseline and Week 12 Visits and dispense necessary supplies. Subjects should collect urine samples at home in accordance with the Urine Collection Instructions and return the collected specimens at the Baseline and Week 12 Visits.

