10.1.7 Baseline Blood Bicarbonate Value Using i-STAT

Blood bicarbonate values are measured onsite using an i-STAT point-of-care device. Baseline blood bicarbonate is defined as the average of the values of blood bicarbonate collected at the Screening 1 Visit, Screening 2 Visit, and Baseline Visit (i.e., Day 1 pre-dose).

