10.1.9 Screening and Baseline eGFR Value

The Screening eGFR value is defined as the average of the values of eGFR used to determine eligibility and calculated from the serum creatinine at the Screening 1 and Screening 2 Visits using the CKD-EPI formula. The creatinine measurements used for determining eligibility may have been analyzed at the central or local laboratory. This Screening eGFR value will be used for the randomization strata.

The Baseline eGFR value is defined as the average of values of eGFR collected at the Screening 1 Visit, Screening 2 Visit, and Baseline Visit (i.e., Day 1 pre-dose), based on serum creatinine measured by the central laboratory. This value will be used for derivation of change from baseline and will serve as a covariate in statistical models.

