10.1.11 Baseline Blood pH and Base Excess Values Using i-STAT

Blood pH and base excess are measured onsite using an i-STAT point-of-care device. The baseline value of each of these two parameters is defined as the average of the measurements collected at the Screening 1 Visit, Screening 2 Visit, and Baseline Visit (i.e., Day 1 pre-dose).

10.1.12 24-hour Urine Excretion of Uric Acid, Sulfate, Creatinine, Albumin, and Urea Nitrogen

If timed urine was collected for more or less than 24 hours, the daily excretion will be normalized and reported as weight unit of the analyte during a 24-hour period.

10.1.13 24-hour Creatinine Clearance

The 24-hour creatinine clearance (mL/min) will be calculated as (urine concentration of creatinine in mg/dL \times urine volume over 24 hours in mL)/(serum creatinine in mg/dL \times 1440).

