Furthermore, in order to examine possible off-target effects of TRC101, the following descriptive summary statistics will be generated:

- CFB in serum potassium for the subset of subjects whose baseline serum potassium is >5.0 mEq/L, any time during the study treatment,
- CFB in serum phosphate for the subset of subjects whose baseline serum phosphate is >5.5 mg/dL, any time during the study treatment, and
- CFB in low density lipoprotein (LDL) for the subset of subjects whose baseline LDL is > 120 mg/dL, any time during the study treatment

Urinalysis results (other than pH and specific gravity), urine microscopic findings, and pregnancy test results will be listed, but not summarized.

From the 24-hour urine collection, the following data will be summarized and listed:

- Change in creatinine clearance (CrCL in mL/min), defined as [24-hour urine volume (mL) * 24 urine Cr (mg/dL)]/[Serum Cr (mg/dL)*1440]
- Change in 24-hour urea nitrogen excretion
- Change in 24-hour albumin excretion
- Change in 24-hour sulfate excretion
- Change in 24-hour uric acid excretion

All laboratory results will be listed. Laboratory results that are above or below normal limits will be flagged in the listings. In addition, laboratory results that meet or exceed the pre-specified levels (i.e., are above [or below as appropriated] the pre-specified levels as shown in the above table) will be flagged.

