15.5 Vital Signs

Descriptive statistics for blood pressure, heart rate, respiratory rate, and temperature, including baseline values and change from baseline values, will be summarized by treatment group and time

point. In addition, number and percentage of subjects with any out of range values (i.e., above a pre-specified level or below a pre-specified level) will be summarized by time point. Tricida chose these pre-specified levels for vital signs because they are more appropriate for the study population than normal ranges for healthy subjects. The pre-specified thresholds levels for vital signs (See Table 5 below).

Table 5 Pre-Specified Threshold Levels for Vital Signs

Vital Sign	Pre-Specified Level
Systolic blood pressure	< 100, > 190 mmHg, > 30% increase or decrease from baseline
Diastolic blood pressure	> 95 mmHg, > 20% increase or decrease from baseline
Heart rate	< 40, > 100 beats/min
Respiratory rate	< 10, > 20 breaths/minute, increase or decrease from baseline by ≥ 6 breaths/minute

All vital signs parameters will be listed. The listing will flag any vital signs that exceed the levels provided in the table above.

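### The high-potassium, high-phosphate and high-LDL subsets are selected on the same single value from which change is measured, so each arm's subset will fall with no drug effect, and the SAP plans no between-arm difference to put that fall in context

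*SAP*

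**What the plan says.** The default in SAP 10.1.6 is: "Baseline values for all efficacy and safety variables are defined as the last non-missing assessment prior to the first dose of study drug", subject to exceptions stated elsewhere. The exceptions are:

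- i-STAT bicarbonate (SAP 10.1.7): "Baseline blood bicarbonate is defined as the average of the values of blood bicarbonate collected at the Screening 1 Visit, Screening 2 Visit" and the Baseline Visit.
- eGFR (SAP 10.1.9): "The Baseline eGFR value is defined as the average of values of eGFR collected at the Screening 1 Visit, Screening 2 Visit, and Baseline Visit".
- i-STAT pH and base excess (SAP 10.1.11), also three-visit averages: "The baseline value of each of these two parameters is defined as the average of the measurements collected at the Screening 1 Visit" and the two later pre-dose visits.
- ECG (SAP 10.1.14), the mean of the Day 1 triplicate.

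No exception covers potassium, phosphate, LDL, creatinine, blood pressure or respiratory rate. SAP 10.1.5 takes "the mean value of multiple measurements collected at the same position" on one visit day, so it does not average across visits.

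The central-laboratory chemistry panel includes potassium, phosphate and LDL (Protocol Table 2). It is drawn at Screening 1, Screening 2 and Day 1 (Protocol 7.1, 7.2, 7.4).

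For possible off-target effects, SAP 15.4 plans descriptive statistics for three subsets. The first is "CFB in serum potassium for the subset of subjects whose baseline serum potassium is >5.0 mEq/L, any time during the study treatment". The other two are phosphate above 5.5 mg/dL and LDL above 120 mg/dL, built the same way. SAP section 15 presents safety statistics by treatment group.

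For vital signs, Protocol Appendix 1 specifies "blood pressure and respiratory rate (both in triplicate, measurements taken approximately 2 minutes apart at Screening 1, Screening 2, and Week 12 Visits", and a single reading at every other time point, including Day 1. SAP Table 5 flags a respiratory-rate "increase or decrease from baseline by ≥ 6 breaths/minute".

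**The concern.** A subject enters one of these subsets because the Day 1 value was high. Part of that height is usually short-term variation, which is not expected to recur at the next draw. Since change is measured from the same draw, the subset mean falls even if the drug does nothing. The direction follows from any within-subject variation at all; only the size needs assumptions.

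The artefact points the same way as the signal being sought. A non-absorbed binder with off-target activity would lower potassium, phosphate or LDL, and the table would show a fall in any case. SAP 15.4 provides no between-arm difference or interval for these subsets, so a reader would see a within-arm fall on TRC101 and have to judge by eye how much of it placebo shares.

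Two smaller matters come from the same default. Week 12 respiratory rate is a mean of three readings but is compared with one Day 1 reading. And in SAP Table 4 the creatinine flag for a rise above 25% uses the last pre-dose value, while eGFR computed from creatinine uses a three-visit mean, so flags from the same sample can disagree because of the baseline alone.

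**Working it through.** No sample size, power or alpha figure in the documents depends on this rule, so there is no stated figure to reproduce.

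**Inputs from the documents.** Cut-offs 5.0, 5.5 and 120 (SAP 15.4); potassium limited to 3.8 to 5.9 mEq/L at both Screening visits (Protocol 4.3, exclusion 14); about 120 and 90 subjects (Protocol 5.2).

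**Assumed, not in the documents.** Potassium mean 4.9, SD 0.5; phosphate mean 4.0, SD 0.8; LDL mean 100, SD 35; correlation r between any two repeat values of 0.5, 0.65 or 0.8; normal values; true change zero.

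**Formula, one baseline value.** With k = (cut − mean)/s,

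expected change = −(1 − r) × s × φ(k)/(1 − Φ(k)).

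- Potassium: k = (5.0 − 4.9)/0.5 = 0.2, ratio 0.391/0.421 = 0.929. At r = 0.5: −0.5 × 0.5 × 0.929 = −0.23. Simulation with the eligibility limits applied gives −0.25.
- Phosphate: k = 1.5/0.8 = 1.875, ratio 2.26. At r = 0.5: −0.5 × 0.8 × 2.26 = −0.91.
- LDL: k = 20/35 = 0.571, ratio 1.19. At r = 0.5: −0.5 × 35 × 1.19 = −20.9.

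**Formula, three-visit mean used for both selection and change.** s₃ = s√(r + (1 − r)/3), k₃ = (cut − mean)/s₃, and expected change = −((1 − r)/3) × (s²/s₃) × φ(k₃)/(1 − Φ(k₃)).

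**Simulated results with no drug effect** (1.5 million subjects per scenario before the potassium limits):

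| | r = 0.5 | r = 0.65 | r = 0.8 |
|---|---|---|---|
| Potassium, single Day 1 value (mEq/L) | −0.25 | −0.18 | −0.10 |
| Potassium, three-visit mean | −0.09 | −0.06 | −0.03 |
| Phosphate, single Day 1 value (mg/dL) | −0.91 | −0.63 | −0.36 |
| Phosphate, three-visit mean | −0.44 | −0.27 | −0.14 |
| LDL, single Day 1 value (mg/dL) | −20.9 | −14.6 | −8.4 |
| LDL, three-visit mean | −9.3 | −5.9 | −3.1 |

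Averaging three visits cuts the fall by about 52% to 71% but does not remove it. Selecting on the Screening 1 and 2 mean and measuring change from Day 1 gives at most 0.001 mEq/L, 0.011 mg/dL and 0.023 mg/dL either side of zero. That result relies on r being the same for every pair of visits.

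**Between arms.** In a null simulation for potassium with 120 and 90 subjects and no eligibility limits, the TRC101 subset fell by 0.09 to 0.23 mEq/L, while TRC101 minus placebo averaged −0.001 (SD 0.06 to 0.10).

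**Subset size.** Under these assumptions about 3% exceed the phosphate cut-off on Day 1: 0.03 × 120 = 3.6 and 0.03 × 90 = 2.7 subjects.

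**Respiratory rate at Week 12.** Let b be the between-visit SD and w the SD of readings within a visit.

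- Single baseline: variance of change = b² + w² + (b² + w²/3).
- Three-visit mean: [2(b² + w²/3) + (b² + w²)]/9 + (b² + w²/3).

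With b = w = 1.5 (assumed) these are 7.50 and 4.17, so SD 2.74 and 2.04. The normal probability of a change of 6 or more either way is 2.8% against 0.3%. Over b = 1.0 to 1.5 and w = 1.0 to 2.0 it is 0.1% to 5.6% against under 0.1% to 0.8%.

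**The case against.** The strongest reply is that the design already deals with this. The trial is randomised, the placebo subset is chosen by the same rule, and both arms are displayed. The null simulation agrees: the difference between arms centres on zero. A reader might infer that the off-target comparison against placebo is biased; the documents do not support that. What stands is narrower. No difference or interval is planned, so the within-arm fall is what the table shows, and in the phosphate subset about three placebo subjects are a weak yardstick.

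The subsets are also an extra display. SAP 15.4 summarises chemistry change for all subjects by arm, without selection on baseline. That is correct and limits the weight of this point.

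Two other inferences go too far. One is that the vital-sign change flags would be mostly noise. Only a null false-flag rate can be computed, it ranges from 0.1% to 5.6% for respiratory rate, and nothing gives the rate of true changes. The other is that the screening readings are thrown away. Systolic readings decide eligibility, all readings are listed, and Screening 2 becomes baseline if Day 1 is missing.

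Nor do the documents support averaging all chemistry and blood pressure across visits. Cystatin C has no screening value (Protocol Table 2). Systolic pressure must be below 170 mmHg in every screening replicate (Protocol 4.2), so averaging those truncated readings into baseline builds in a small rise: about 0.2 to 0.4 mmHg when simulated with an assumed mean of 135 to 140, between-subject SD of 15 to 18, between-visit SD of 8 and within-visit SD of 6. There is also a reason to treat bicarbonate and eGFR differently: averaged bicarbonate is the eligibility measure, and both are model covariates.

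**Conclusion.** The point holds for the three off-target subsets in SAP 15.4. Selection and change share one pre-dose value, so each arm's subset is expected to fall without any drug effect, by about 0.10 to 0.25 mEq/L potassium, 0.4 to 0.9 mg/dL phosphate and 8 to 21 mg/dL LDL. These sizes rest on the assumed means, SDs and correlations of 0.5 to 0.8; the direction does not.

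The consequence is a risk of misreading a within-arm fall on TRC101 as off-target binding. It is not a bias in the comparison with placebo. The affected outputs are descriptive safety summaries. The primary and secondary endpoints use the three-visit bicarbonate baseline and are not touched.

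The respiratory-rate baseline and the mismatch between the creatinine and eGFR baselines are secondary and smaller.

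**What to change.** In SAP 15.4:

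1. Define the three subsets on the mean of the Screening 1 and Screening 2 central-laboratory values, using the one available if the other is missing.
2. Compute change from the Day 1 pre-dose value.
3. Beside each within-arm change, report the subset count and the TRC101-minus-placebo difference with a 95% CI.

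Step 3 is also the safeguard if values drift or correlations weaken with time, in which case steps 1 and 2 would not remove the fall completely.

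As smaller changes, set the respiratory-rate baseline to the mean of the Screening 1, Screening 2 and Day 1 visit means, and base the creatinine flag in Table 4 on the same three-visit central-laboratory baseline as creatinine-based eGFR. Leave the default in SAP 10.1.6 for other chemistry and for blood pressure.

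The cost is SAP wording and programming, since all the values are already collected. Subset membership and creatinine flag counts will shift slightly, and the subset definition will differ from the default baseline, which needs a table footnote. The phosphate subset gets smaller still: about 1.5% to 2.4% under the assumptions above, or 1.8 to 2.9 subjects of 120 and 1.4 to 2.2 of 90. Its interval may be uninformative or not estimable, and individual values may serve better there.

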10.1.7 Baseline Blood Bicarbonate Value Using i-STAT

Blood bicarbonate values are measured onsite using an i-STAT point-of-care device. Baseline blood bicarbonate is defined as the average of the values of blood bicarbonate collected at the Screening 1 Visit, Screening 2 Visit, and Baseline Visit (i.e., Day 1 pre-dose).

10.1.8 Baseline Blood Bicarbonate Subgroups

For exploratory efficacy analysis, subjects will be classified according to their baseline blood bicarbonate stratum (≤ 18 mEq/L or >18 mEq/L).

10.1.9 Screening and Baseline eGFR Value

The Screening eGFR value is defined as the average of the values of eGFR used to determine eligibility and calculated from the serum creatinine at the Screening 1 and Screening 2 Visits using the CKD-EPI formula. The creatinine measurements used for determining eligibility may have been analyzed at the central or local laboratory. This Screening eGFR value will be used for the randomization strata.

The Baseline eGFR value is defined as the average of values of eGFR collected at the Screening 1 Visit, Screening 2 Visit, and Baseline Visit (i.e., Day 1 pre-dose), based on serum creatinine measured by the central laboratory. This value will be used for derivation of change from baseline and will serve as a covariate in statistical models.

10.1.10 Screening eGFR Subgroups

For exploratory efficacy analysis and/or safety analysis, subjects will be classified according to their Screening eGFR stratum. The Screening eGFR subgroups are:

- $<30 \text{ mL/min}/1.73\text{m}^2$
- $\geq30 \text{ mL/min}/1.73\text{m}^2$

10.1.11 Baseline Blood pH and Base Excess Values Using i-STAT

Blood pH and base excess are measured onsite using an i-STAT point-of-care device. The baseline value of each of these two parameters is defined as the average of the measurements collected at the Screening 1 Visit, Screening 2 Visit, and Baseline Visit (i.e., Day 1 pre-dose).

10.1.12 24-hour Urine Excretion of Uric Acid, Sulfate, Creatinine, Albumin, and Urea Nitrogen

If timed urine was collected for more or less than 24 hours, the daily excretion will be normalized and reported as weight unit of the analyte during a 24-hour period.

10.1.13 24-hour Creatinine Clearance

The 24-hour creatinine clearance (mL/min) will be calculated as (urine concentration of creatinine in mg/dL \times urine volume over 24 hours in mL)/(serum creatinine in mg/dL \times 1440).

10.1.14 Baseline Electrocardiogram Parameters

12-lead ECG parameters will be collected in triplicate on Day 1 pre-dose. The average of the ECG intervals and heart rate measurements will be used as baseline. Screening values will be used as baseline for subjects who did not have any ECG measurements on Day 1 pre-dose.

10.1.15 Treatment-Emergent Adverse Events

Treatment-emergent adverse events (TEAEs) are defined as all AEs that begin on or after the time of the first dose of study drug (also see Section 11.4.1). Related AEs are those reported by investigators as possibly related, probably related, or related to study drug.

10.1.16 Concomitant Medications and Concurrent Procedures

Prior medications are defined as all prescription and over-the-counter medications that were taken within 28 days (whether continuing or not) prior to the study drug administration. Concomitant medications are defined as all prescription and over-the-counter medications that are used concurrently (from Day 1 to Week 14). A prior medication can also be a concomitant medication if it continued after the first dose of study drug.

10.1.17 Alkali Therapy

Oral alkali therapies are medications containing active ingredients of sodium bicarbonate, potassium bicarbonate, potassium citrate, or sodium citrate. Baseline alkali therapies are those medications that were used at the start of study treatment.

10.2 Analysis Windows

Clinical visits may occur outside protocol-specified windows. Therefore, instead of relying solely on visit labels in the clinical database, analysis visits and their windows are defined using Study Day (See Section 10.1.2). For the purposes of data analysis and summary, assessments and/or measurements will be flagged based on the collection date/time that is closest to the protocol-scheduled time point (or target Study Day). Analysis visit windows are presented in Table 2 by type of assessments and/or measurements.

Table 2 Analysis Visit Windows

Protocol Scheduled Time Point	Target Study Day	Analysis Visit Windows (Study Day)					
		All Other Assessments	Hematology Urinalysis Spot Urine Pregnancy Tests	Repeated Chair Stand KDQOL Biomarkers	24-Hour Urine Collection	ECG	Body Weight
Screening 1	-14	$\leq -8^*$	$\leq -8^*$	-	-	-	-
Screening 2	-1	-7 to -1*	-	-	-	-	-
Day 1	1	1*	-7 to 1*	-14 to 1*	-14 to 1*	-	$\leq 1^*$
Week 1	8	2 to 11	-	-	-	-	-
Week 2	15	12 to 22	-	-	-	2 to 28	-
Week 4	29	23 to 36	-	-	-	-	2 to 42
Week 6	43	37 to 50	2 to 63	-	-	29 to 63	-
Week 8	57	51 to 64	-	-	-	-	43 to 70
Week 10	71	65 to 78	-	-	-	-	-
Week 12	85	79 to 90	64 to 91	≥ 2	64 to 91	71 to 91	-
Week 13	92	91 to 97	-	-	-	-	-
Week 14	99	≥ 98	≥ 92	-	-	≥ 92	≥ 92

* Use visit designation for scheduled visits; otherwise use the visit window.

